**Central Neck Dissection in Patients with
Clinical Node Negative Thyroid Cancer**

Authors:

[name]

Principal Investigator

University of Wisconsin-Madison

&

[name]

Co-Principal Investigator

University of Wisconsin-Madison

NCT02138214

Original Protocol Version Date: 12-Mar-2014

Revision 1 Date: 18-Apr-2014

Revision 2 Date: 04-Sep-2014

Revision 3 Date: 16-Feb-2015

Revision 4 Date: 06-Apr-2015

Revision 5 Date: 14-Sep-2015

Revision 6 Date: 23-Oct-2015

Revision 7 Date: 01-May-2016

Revision 8 Date: 20-Dec-2016

Revision 9 Date: 06-Oct-2017

Revision 10 Date: 22-Feb-2018

Revision 11 Date: 19-Jul-2018

Revision 12 Date: 13-Sep-2018

Revision 13 Date: 17-Jan-2020

[figure not shown]
HSIRB# 2014-0391 (UW13115)

Summary

Thyroid cancer is usually treated with the complete surgical removal of the thyroid gland, but due to concerns that the cancer may recur in the future, lymph nodes in the central part of the neck may also be surgically removed. Unfortunately, the additional lymph node surgery may be associated with increased risks for complications such as inadequate calcium, problems with voice function, swallowing deficits, and generally diminished quality of life. Because the risks for these complications are poorly defined, we propose to do a clinical trial where we will compare clinical recurrence rates and complication levels in patients with papillary thyroid cancer who have thyroid gland removal alone to those who receive thyroid gland removal plus lymph node surgery in the central neck.

In this clinical trial, 70 - 140 patients undergoing surgery treatment for thyroid cancer will be enrolled into one of three treatment arms. Patients receiving total thyroidectomy for papillary thyroid cancer (PTC) with no pre-operative evidence of distant or cervical lymph node metastasis will be randomized into one of two arms: prophylactic central neck dissection or no central neck dissection. Patients who are not eligible for randomization will be enrolled into a third standard of care arm. We will then compare the three cohorts: (1) To determine the rate of transient and persistent hypocalcemia; (2) To determine the rate of voice and swallowing problems; (3) To determine the degree to which HR-QOL is compromised; (4) To determine clinical recurrence rates; (5) To determine the degree to which Natural Language Processing (NLP) tools can extract and document quality of life measures from patient interview narratives; (6) To determine the extent of correlation among quality of life measures obtained from patient interview narratives and those from traditionally administered quality of life surveys.

Figure 1: Trial overview diagram

Schedule of activities

	Visit 1	Visit 2	Visit 3	Visit 4	Visit 5		Visit 6	Visit 7	
	Screening	Day of Operation	Post-Op	Day 12	Week 6	Cancer Screen	Month 6	1 Year	Follow-up
Window	6 weeks-24 hours before operation		0-2 days	± 8 days	4-20 weeks	+2-7 days after Week 6	±6 weeks ¹	10 – 18 months	+10-19 months (+1-6 weeks post 1 year)
Informed Consent Obtained	X								
Venipuncture	SOC		SOC	SOC	SOC	SOC ^{2, 3, 4}	CI	SOC	
Calcium ³	SOC ³		SOC ^{3, 5}	SOC ^{3, 5}			X ^{5, 17}	CI ^{5, 17, 18}	
Parathyroid Hormone (PTH) ³	SOC ³		SOC ^{3, 5}	SOC ^{3, 5}			X ^{5, 17}	CI ^{5, 17, 18}	
Vitamin D ¹⁷	CI ^{6, 17}								
Neck Ultrasound	SOC ⁷						SOC	SOC	
Chest X-ray ⁸	SOC ⁸								
Comprehensive Voice Evaluation: Phonation Threshold Pressure, Dysphonia Symptom Index, CAPE-V, GRBAS, Stroboscopy, Glottal Function Index, VHI	CI ⁹			CI ⁹	CI ¹⁰		CI ¹⁰	CI ¹⁰	
Swallow Evaluation: standardized videofluoroscopic swallow study ¹⁵	X ¹¹			CI ¹¹	CI ¹¹		CI ¹¹	CI ¹¹	
Quality of Life Surveys, including: (1) the Short Form 12 (SF-12, Medical Outcomes Trust); (2) The European Organization for Research and Treatment of Cancer QOL instrument (EORTC QLQ C30); (3) The Voice Handicap Index (VHI) for assessing voice-related QOL (part of voice evaluation); (4) the EAT-10 Swallow Instrument; (5) Thyroid Cancer QOL (Thy-Ca QOL)	X			X	X		X	X	
Interviews (Audio Recorded)	X			X	X		X	X	
Participant Receives Symptom Log ^{3, 12}	X ^{3, 12}								
Randomization ¹³	X ¹³								
Enrolled	X								
Adverse Events Monitoring	X		X	X			X	X	
Endocrine Consult ¹⁴			SOC ¹⁴						
Participant Returns Symptom Log & it is Reviewed ³			X ³						
Participant & Study Staff Unblinded			X						
Unstimulated Thyroglobulin ¹⁵				SOC ^{15, 16}			SOC ¹⁵	SOC ¹⁵	
Stimulated Thyroglobulin ¹⁵					SOC ^{2, 15}	SOC ¹⁵	SOC ¹⁵	SOC ¹⁵	
Radioactive iodine (RAI) Whole Body Scan ²					SOC ²		CI ⁴		
QI follow-up survey is administered via email									X

Procedure Key: **SOC** = performed as needed per Standard of Care; **X** = Research Only; **CI** = Clinically Indicated (performed SOC if warranted by patient's condition, otherwise the procedure will be done as part of research)

¹The Month 6 time point must occur at least 4 weeks after the RAI is given, if applicable.

²Patients with an elevated unstimulated thyroglobulin level (>2 ng/mL) at Week 6 and/or an intermediate or high risk level will be evaluated for standard of care radioactive iodine ablation therapy and corresponding TSH stimulated thyroglobulin lab and radioactive iodine whole body scan.

³Only patients who receive at least a total thyroidectomy (e.g. total thyroidectomy with central neck dissection, total thyroidectomy with lateral neck dissection)

⁴If Thyroglobulin >2ng/ml and neck US is negative (**randomized patients only**)

⁵All participants will be asked to stop their calcium and calcitriol supplementation 12 hours prior to their follow up appointment(s) so that a repeat calcium and PTH level can be checked.

⁶Vitamin D is clinically indicated if PTH is elevated or calcium is low.

⁷Ultrasounds within three months of surgery can be used for screening purposes.

⁸CXR only performed as needed at screening to rule out metastases.

⁹Voice evaluations are routinely performed pre-operatively in patients with prior neck surgery or voice complaints and post-operatively in anyone with a voice concern.

¹⁰Evaluations will only be obtained if results are abnormal at previous evaluation.

¹¹Swallow studies were eliminated as of 12/01/2016.

¹²Between Visits 2 and 4, participants will be asked to record daily any symptoms which they think may be related to hypocalcemia (paresthesias, muscle cramps, etc). They will be asked to describe the symptoms and mark the time that the symptoms occurred and the severity of the symptoms (graded on a scale of 1-5). They will record the doses of calcium administered and how long it took the symptoms to resolve. Participants will total their daily calcium intakes. They will be instructed to contact us if they are requiring greater than 8 g /day and in such instances will be started on calcitriol 0.25 mcg twice daily to increase their intestinal calcium absorption.

¹³Randomization only performed for patients receiving total thyroidectomy with histologically confirmed diagnosis of PTC and no evidence of metastases.

¹⁴Only patients with histologically confirmed cancer diagnosis. Consult will occur at approximately two weeks after surgery for patients who receive total thyroidectomy and at approximately six to eight weeks after surgery for those who receive partial thyroidectomy.

¹⁵Thyroglobulin determinations will also include anti-thyroglobulin antibody.

¹⁶An unstimulated thyroglobulin level will be obtained at Week 6 to assist in decision making regarding the necessity for radioactive iodine ablation therapy.

¹⁷Randomization patients only. Patients enrolled into the standard of care arm will not receive special labs for research only.

Table of Contents

Summary.....	2
Trial overview diagram.....	3
Schedule of activities	4
List of abbreviations and definitions.....	6
1. Introduction.....	8
1.1. Background.....	8
1.2. Rationale and hypothesis	9
2. Objectives.....	9
2.1. Primary outcome and endpoints.....	9
2.2. Secondary outcomes and endpoints	10
3. Study design	11
4. Study population.....	16
4.1. Inclusion criteria	16
4.2. Exclusion criteria.....	16
4.3. Intra-operation exclusion criteria.....	16
4.4. Protected populations	16
5. Trial interventions.....	16
5.1. Treatment Arm 1, Group 1 (No CND)	16
5.2. Treatment Arm 2, Group 2 (CND).....	16
5.3. Allocation to intervention.....	16
6. Participant recruitment and consent.....	17
6.1. Participant identification	17
6.2. Screening	17
6.3. Recruitment and consent	17
7. Activities and measurements.....	18
7.1. Table: Time points for data collection.....	19
7.2. Blood sample collection.....	21
7.3. Data entry.....	21
7.4. Participant withdrawals.....	21
7.5. Stopping rules	22
8. Data analysis and statistical considerations.....	22
8.1. Sample size determination	22
8.2. Analysis of endpoints.....	23
9. Risks and benefits of trial participation	23
9.1. Potential risks	24
9.2. Mitigation of potential risks	25
9.3. Potential benefits and risk-to-benefit ratio.....	26
10. Adverse events and unanticipated problems.....	27
10.1. Adverse event definitions.....	27
10.2. Severity assessment	27
10.3. Causality assessment	27
10.4. Procedures for recording and reporting adverse events	27

11. Trial safety monitoring	28
11.1. Data Safety Monitoring Committee	28
11.2. Review and oversight requirements.....	29
11.3. Expedited reporting of Serious Adverse Events	30
12. Administrative requirements.....	33
12.1. Good clinical practice	33
12.2. Data quality assurance	33
12.3. Study monitoring	33
12.4. Ethical consideration	33
12.5. Patient confidentiality	33
12.6. Investigator compliance	34
12.7. Participant cost and payment.....	34
13. Funding sources	34
14. Publication policy	34

List of abbreviations and definitions

AE	Adverse event
ATA	American Thyroid Association
CAPE-V	Consensus Auditory Perceptual Evaluation of Voice
CND	Central neck dissection
CRF	Case report form
CXR	Chest x-ray
DMC	Data Monitoring Committee
EORTC	European Organization Research Treatment of Cancer
eCRF	Electronic case report form
EDC	Electronic data capture
FNA	Fine needle aspiration
HR-QOL	Health related quality of life
IRB	The institutional review board of record for the study
MSC	Mental Component Score
PCS	Physical Component Score
Permanent hypoparathyroidism	Defined as the need for either calcium or calcitriol to prevent symptoms of hypocalcemia or a serum calcium <8.0 mg/dL with a PTH <15 pg/mL at 6 months post-operatively
PRMC	Protocol Review Monitoring Committee
PTH	Parathyroid hormone
PTC	Papillary thyroid cancer
QOL	Quality of life
rTSH	Recombinant thyroid-stimulating hormone
RAI	Radioactive iodine
SAE	Serious adverse event
SOC	Standard of care
Tg	Thyroglobulin
ThyCa-QOL	Thyroid Cancer Quality of Life
UW	University of Wisconsin
VHI	Voice Handicap Index

1. Introduction

1.1. **Background**

Each year in the United States 46,670 new cases of thyroid cancer are diagnosed. The incidence of thyroid cancer in the United States has increased nearly 2.4-fold from 1950 to 2000. It is therefore critically important that treatments for this disease are grounded in high levels of research evidence.

Currently, complete removal of the thyroid (total thyroidectomy) is the primary treatment for papillary thyroid cancer (PTC). A prophylactic (preventative) central neck dissection to remove the lymph nodes near the thyroid is also often performed along with the total thyroidectomy.

A therapeutic central neck dissection (CND) is performed if there is evidence of lymph node involvement on pre-operative ultrasound or on intra-operative inspection. The removal of clearly involved lymph nodes is believed to provide a therapeutic benefit and to aid in local control of disease.

A prophylactic CND is somewhat different because it involves removing lymph nodes that are empirically *normal* on imaging and inspection with the belief that they may contain nascent disease, and if removed, will decrease the risk of recurrence. It is well established that central neck lymph nodes harbor microscopic lymph node involvement in 60% of cases. However, it has never been shown in a prospective study that prophylactic CND decreases recurrence or improves survival.

The role of prophylactic CND is one of the biggest clinical questions in the management of thyroid cancer today. With over 280 retrospective studies and reviews trying to address this question, there is still no consensus as to whether or not this procedure offers any real benefits. Instead, this procedure may place the patient at risk for serious and pervasive deficits in communicative function, nutrition, hydration, and health related quality of life (HR-QOL). Hypoparathyroidism can also result and may lead to life-threatening hypocalcemia that requires medications four or more times a day. These complications can be devastating, especially for young patients who will have to accommodate these consequences for the rest of their lives. However, removal of lymph nodes by means of a prophylactic CND at the initial operation may decrease the need for repeat surgery and its associated higher risks.

This debate came to the forefront when the American Thyroid Association (ATA) issued consensus guidelines in 2006 that recommended consideration of a prophylactic CND in all patients with thyroid cancer. These guidelines were based on retrospective studies using historical controls because higher levels of evidence were lacking. After the guidelines were published, there was a flurry of further retrospective studies performed in attempt to either support or refute that recommendation. The 2006 ATA practice guidelines were partially revised in 2009 to “recommend,” based on expert opinion, an even lower level of evidence than the retrospective study designs found in the previous literature. Unfortunately, there remain limited data to either support or refute the 2009 recommendation.

The randomization arms will compare two accepted standards of care in a Phase II clinical trial. Both surgical procedures are widely practiced in the United States for the treatment of thyroid cancer, and it is not known which procedure is best. A prophylactic CND may be associated with a higher complication rate but may also provide a clinically relevant reduction in disease recurrence. Retrospective reviews have been unable to come to a consensus to answer this question adequately. In order to determine the optimal surgical management for patients with clinically node negative thyroid cancer, a randomized clinical trial is needed. A recent clinical trials planning meeting held at the National Cancer Institute picked the issue of prophylactic central neck dissection as the area of thyroid cancer that most needs a

randomized controlled trial. Since not all patients will be eligible for randomization but could provide valuable information about the impact of surgery and surgical complications on quality of life, we would like to offer patients not eligible for the randomization arms or those that are unable to be randomized intraoperatively the ability to participate in the study in the SOC arm.

Background on Natural Language Processing of patient interview narratives:

Traditionally, clinicians and researchers measure quality of life using one of several structured quality of life surveys. Such tools can become time-consuming and expensive to employ for research or clinical use. Furthermore, these surveys require patients to answer structured questionnaires about their health rather than to simply describe their experience in a more natural, narrative format.

Patient use of electronic health resources and health-related social media sites has increased significantly in the past few years. These resources offer the opportunity for patients to share their experiences in a more natural, narrative format. Making this existing information available to clinicians in a validated, standardized format will result in: 1) improved communication between patient and physician, 2) efficient longitudinal tracking of quality of life measures within an electronic medical record, and 3) retrieval and coding of quality of life data contained in narrative social media content. By applying Natural Language Processing (NLP) techniques to patient narratives collected in our qualitative interviews, we will be able to see if patients' natural language be linked to changes in their overall quality of life or other factors that could affect patient care.

1.2. Rationale and hypothesis

We propose a clinical trial in which 70 - 140 patients undergoing surgery for PTC with no pre-operative evidence of distant metastasis will be enrolled into one of three treatment arms: total thyroidectomy with prophylactic central neck dissection, total thyroidectomy without central neck dissection or standard of care. The total thyroidectomy patients will be randomized into one of the first two arms. The standard of care patients, patients who are not eligible for the randomization arms pre-operatively or are unable to be randomized intraoperatively, will be enrolled into the third study arm and will not have any aspect of their cancer care modified by study participation but will otherwise follow the same follow up study assessment schedule as the patients in the randomization arms. In the absence of this clinical trial, patients seen at our center would be offered a total thyroidectomy without central neck dissection, which is our current practice standard. At many other major academic centers, however, a prophylactic central neck dissection is the standard of care. Currently about 50% of high volume institutions are doing a central neck dissection routinely in their practice. While performing a central neck dissection may increase the risks of surgery it may also decrease the risk of recurrence. We do not know, given the presently available data, which will be greater, and therefore this study has true clinical equipoise.

Our hypothesis is that total thyroidectomy with prophylactic central neck dissection will result in a higher complication rate in comparison with total thyroidectomy alone for papillary thyroid cancer.

2. Objectives

2.1. Primary outcome and endpoints

To determine the rate of transient and permanent hypocalcemia:

- Transient hypoparathyroidism as defined by a Day 1 serum parathyroid hormone (PTH) level of <10 pg/ml
- Post-operative serum calcium (mg/dL) and PTH (pg/ml) at Day 12 and Month 6

- Total calcium consumption in first 2 weeks (total gm)
- Hypocalcemia symptoms in first 2 weeks (average episodes/day)
- Hypocalcemia symptom severity scale (range of 1-5)
- Requirement for calcium and calcitriol at Month 6 (or, if laboratory values at visit reveal calcium < 8 mg/dL and PTH <15 pg/ml)

Calcium and PTH levels, calcium intake, and hypocalcemia symptoms will be monitored post-operatively (at Day 1, Day 12, and Month 6) to examine how parathyroid function is affected by a CND.

Hypoparathyroidism can lead to paresthesias and muscle cramps and is a known complication of total thyroidectomy, requiring frequent treatment with calcium and vitamin D. This risk is increased with a CND and is thus important to quantify when examining the risk/benefit ratio. Because calcium supplementation is routinely administered for symptoms of hypocalcemia in the post-operative period and this may impact the interpretation of laboratory evaluations, we will be evaluating a variety of metrics to assess the incidence and impact of hypocalcemia on patients.

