Eligible patients will have a thyroid nodule >1 cm in size that is consistent with or suspicious for PTC on a pre-operative biopsy. All biopsies will be reviewed by pathology to confirm eligibility. Patients with T4 (tumor of any size that extends beyond the thyroid) tumors, history of degenerative neurological diseases, pre-operative vocal cord paralysis or other vocal cord pathology will be excluded. All patients will undergo a comprehensive neck ultrasound to evaluate for lymphadenopathy by an experienced thyroid radiologist. A comprehensive evaluation of lymph nodes in levels 1-6 will be performed. If the patient is proven to have lymph node involvement they will be ineligible for the randomization arms.

Patients without evidence of nodal involvement on pre-operative imaging will be eligible for the randomization arms of the trial and consented pre-operatively. Per standard of care at our institution and the recommendations of the ATA, thyroid cancer patients are offered various surgical treatments depending on the nature of their disease. For example, for those whose cancer is limited to only one side of the thyroid, a partial lobectomy may be the appropriate treatment. For this reason, we will only approach patients who have elected to undergo total thyroidectomy for the randomization arms. Patients who are eligible for the trial but not for randomization (i.e. have evidence of lymph node disease or are choosing a thyroid lobectomy) will be approached for consent into the standard of care arm.

Pre-Operative Screening and Testing: Pre-operative laboratory testing will include calcium, PTH, and Vitamin D testing (Aim 1), a comprehensive voice and swallow¹ evaluation (Aim 2), and a complete quality of life evaluation using validated questionnaires and semi-structured interviews (Aim 3). Patients eligible for the randomization arms will then be randomly assigned - after intraoperative confirmation of no suspicious adenopathy or gross local invasion - to one of two treatments on the day of surgery; Arm 1: total thyroidectomy alone, or Arm 2: total thyroidectomy with ipsilateral prophylactic CND. Randomization will be stratified by both age and tumor size to allow appropriate comparisons between groups. Allocation schedule will not be known to study staff prior to consenting.

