8.1. Sample size determination

At the beginning of this study, we anticipated randomizing 140 patients with clinically node negative thyroid cancer, with the goal of 116 participants completing the study. Patients will be recruited from the Endocrine Surgery and Otolaryngology Clinics at the University of Wisconsin Hospitals and Clinics. This is a high volume tertiary care center with a large thyroid practice, performing approximately 350 thyroid operations per year. Thyroid cancer accounts for 30% of thyroidectomy cases at our institution and this is the pool from which the patients will be identified (approximately 105 patients/year). Approximately 15% of thyroid cancer cases will have a positive pre-operative ultrasound, thus decreasing our pool of eligible participants to approximately 89 patients per year. With an accrual goal of 140 participants within 4 years, we would need to recruit 39% of eligible patients each year.

Permanent complications in thyroid surgery are uncommon, but these complications can be disastrous for a patient that is affected. Permanent hypoparathyroidism occurs in 1-2% of patients after a total thyroidectomy and the risk may be as high as 14% when a CND is performed. The best surrogate marker to predict an increase in permanent morbidity is the incidence of transient hypoparathyroidism, which is substantially more common than permanent hypoparathyroidism. For example, transient hypoparathyroidism occurred in 12% of our last 270 patients undergoing a total thyroidectomy. The rate of transient hypoparathyroidism in patients treated with a CND has been shown in the literature to be significantly higher. The rate of transient hypoparathyroidism in recent large retrospective studies was reported to be between 38-51%.

We assumed a power of 0.8 and an alpha of 0.05. For sample size calculations we made the assumption that the incidence of transient hypoparathyroidism after a total thyroidectomy alone is 12% and that an increase to 36% (or tripling of the risk) is clinically significant. The rate of hypoparathyroidism in Arm 1 is based upon our last 270 patients and is a reliable estimate. The incidence in the CND arm is based on a

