review of the literature and we purposely chose a number on the lower end of quoted ranges to ensure that we are not underestimating our sample size. With these assumptions the sample size is 116, with 58 patients per arm. Due to the short follow up for our primary endpoint (post-operative day 1) and for our secondary endpoints (<12 months), we anticipate no significant loss to follow up. For our secondary aims, we chose the Dysphonia Severity Index (DSI) as representative and found a prior thyroid surgery study (45) showing that as few as 8 patients in a negative voice outcome group were sufficient to detect clinically meaningful differences on this measure versus patients with normal vocal functioning at 6 months post-op. Thus, the sample size in our study should be adequate to address our secondary aims even if there is attrition/ loss to follow-up.

The number of patients who must be consented will be larger than the final sample size because a portion of patients that are enrolled and evaluated pre-operatively may not be randomized the day of surgery (because malignancy is not proven intraoperatively, suspicious adenopathy is identified, or there is gross local invasion). We aim to increase the sample size by 20% to accommodate for this.

We have found in our examination of preliminary data that our objective measures are not effectively capturing the impact of surgery on patients and that the most critical and meaningful data that we are obtaining from our study is from the in-depth patient interviews. Given the value of our qualitative data, we need to ensure that we are capturing adequate qualitative data to identify differences between the objective and patient-reported evaluations of experiences with hypocalcemia and voice and swallowing problems caused by transient or permanent nerve injury. Ultimately, we plan to make our existing study aims even more robust by incorporating both objective and subjective data into each of our primary and secondary outcomes measures.

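### Day 1 PTH, on which the trial was sized, is an endpoint only as below 10 pg/ml; with a floor of 70 randomized, a pre-specified supportive analysis of the measured value is worth adding

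*Combined protocol and SAP*

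**What the plan says.** Section 2.1 gives the Day 1 endpoint as "Transient hypoparathyroidism as defined by a Day 1 serum parathyroid hormone (PTH) level of <10 pg/ml". The next item lists laboratory values as endpoints, but only at later visits: "Post-operative serum calcium (mg/dL) and PTH (pg/ml) at Day 12 and Month 6". The same section adds a general statement: "Calcium and PTH levels, calcium intake, and hypocalcemia symptoms will be monitored post-operatively (at Day 1, Day 12, and Month 6".

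Section 8.1 sizes the trial on the yes/no Day 1 endpoint. It assumes "the incidence of transient hypoparathyroidism after a total thyroidectomy alone is 12% and that an increase to 36% (or tripling of the risk", states "We assumed a power of 0.8 and an alpha of 0.05", and concludes "With these assumptions the sample size is 116, with 58 patients per arm". It then sets the target at 70 to 140 randomized. The lower figure is justified by the amount of interview data needed, and power for the Day 1 endpoint is not recomputed.

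Section 8.2 plans a mixed-model ANOVA for all primary aims, with transformation or nonparametric methods where assumptions fail. Its time levels are pre-surgery, Day 12 and the later visits. Day 1 is not among them, and no test is named for a binary endpoint.

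The samples exist. Section 3 says "Pre-operative laboratory testing will include calcium, PTH, and Vitamin D testing", and the table in section 7.1 schedules PTH before surgery and on Day 1.

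**The concern.** The endpoint that fixed the sample size is a laboratory measurement cut at one value. On the yes/no scale, a patient whose PTH falls from 50 to 11 pg/ml counts the same as one with no fall. Cutting a continuous measure often costs power, and that matters more now that the trial may stop at 70 randomized patients instead of the 116 that the sizing required.

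Without a specified numeric analysis, the trial could reach its floor with an inconclusive comparison of rates and no pre-planned way to use the rest of the Day 1 data. A numeric analysis chosen after a non-significant binary result would carry little weight.

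**Working it through.** **Inputs from the documents.** Rates 12% and 36%, alpha 0.05, power 0.80, 58 per arm, target 70 to 140 randomized (all section 8.1); cut at 10 pg/ml (section 2.1). Sidedness is not stated; two-sided is assumed because it reproduces the stated size.

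**Step 1: the plan's own figure.** With mean rate 0.24 and difference 0.24:

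- Uncorrected: n = [1.960·√(2·0.24·0.76) + 0.842·√(0.12·0.88 + 0.36·0.64)]² / 0.24² = 48.5, so 49 per arm.
- Continuity-corrected: n = (48.5/4)·[1 + √(1 + 4/(48.5·0.24))]² = 56.5, so 57 per arm or 114 in total, close to the stated 116.

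**Step 2: power of the yes/no endpoint.** Exact binomial enumeration, 12% vs 36%, two-sided 0.05:

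| Per arm | Fisher | Chi-square |
|---|---|---|
| 35 | 57% | 66% |
| 58 | 83% | 88% |

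This step uses only the protocol's rates. The Summary and section 1.2 can also be read as 70 to 140 patients across three arms. At about 23 per arm (an assumption), power would be 38% (Fisher) to 50% (chi-square).

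**Step 3: power of the measured value under one model.** The documents give no mean, SD or shape for Day 1 PTH. Assume that PTH, perhaps on a log scale, is normal with equal SD in both arms and that CND shifts it down. The shift that yields 12% and 36% below the cut is z(0.36) − z(0.12) = −0.358 − (−1.175) = 0.817 SD.

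- t-test (noncentral t): 92% at 35 per arm, 99% at 58.
- Rank test: 90-91% at 35 per arm. It stays at about 90% if every value below the cut is tied, so values at an assay floor do not remove the gain.
- Adjusted for pre-operative PTH with an assumed correlation r, the effective shift is 0.817/√(1 − r²). That is 0.856 at r = 0.3 and 0.943 at r = 0.5, giving 94% and 97% at 35 per arm.
- For 80% power the value needs 24 to 25 per arm, against 49 (uncorrected) or 57 (corrected) on the yes/no scale. The information lost to the cut is then 1 − 24.5/49 = 50% to 1 − 24/57 = 58%.

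**Step 4: other models with the same 12% and 36%.** Rank test, 35 per arm, by simulation:

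- SD ratio CND/no CND of 1.25. The CND mean is −1.175 + 1.25·0.358 = −0.727 in no-CND SD units: power about 73-74%.
- SD ratio 1.5. The mean is −1.175 + 1.5·0.358 = −0.637: power about 51-52%.
- Subset effect. A fraction 0.24/0.88 = 27% of those who would otherwise be above the cut fall below it, and the rest are unchanged: power about 41-43%.

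In the last two cases the measured value does worse than either binary test.

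**The case against.** The best case for leaving the plan alone has four parts, each of which checks a stronger reading.

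- A reader might infer that Day 1 PTH is used only as a yes/no. Section 2.1 says Day 1 levels will be monitored to see how CND affects parathyroid function, and section 7.1 records the value. The documents therefore support only this: no numeric Day 1 endpoint or analysis is specified.
- A reader might infer that pre-operative PTH goes unused. Section 8.2 has a pre-surgery level, so baseline PTH can enter the model for the later values. What is missing is its use with the Day 1 value.
- A reader might infer that supplementation spoils the later PTH values. Section 2.1 does raise the problem, but it gives that as its reason for using several metrics. Footnote 5 of the schedule asks participants to stop calcium and calcitriol 12 hours before follow-up. The concern is partly met.
- A reader might infer that the cut discards most of the information. That rests on an equal-SD shift that nothing in the documents establishes. A subset effect is plausible, since the dissection is ipsilateral and section 3 has glands preserved in place, or autotransplanted if devascularized.

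The two scales also answer different questions. The stated objective is a rate, and a difference in PTH units may lie partly within non-deficient values. A supportive numeric analysis leaves the power of the binary endpoint at 70 patients unchanged.

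All of this stands as a limit on the claim. It does not remove the gap, because an intention to monitor is not an analysis, and section 8.2 leaves Day 1 out.

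**Conclusion.** The point holds as an inexpensive improvement. The plan defines the sizing endpoint on one side of a cut, specifies no analysis of the number behind it, and allows the trial to finish at a size where the yes/no comparison has about 57-66% power at the protocol's own rates.

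How much the measured value would add cannot be settled from the documents. Under an equal-SD normal shift of 0.82 SD, power at 35 per arm is about 90-92%, or 94-97% with baseline adjustment at an assumed correlation of 0.3 to 0.5. With a more variable CND arm the gain falls away and can turn negative, and with a subset-only effect it is negative. The numeric analysis is therefore justified beside the rate and not in its place.

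**What to change.** Keep the Day 1 rate below 10 pg/ml, with its 95% CI, as the clinical endpoint.

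Add one line to section 2.1 naming Day 1 PTH as measured, and one sentence to section 8.2 that:

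- specifies a proportional-odds or rank-based comparison of the randomized arms, so that values at the assay floor are handled;
- adjusts for pre-operative PTH;
- reports the arm difference with its 95% CI;
- labels the analysis supportive and places it after the binary endpoint in the multiplicity order. Section 8.2 promises an alpha adjustment but gives no order.

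The same edit should bring Day 1 into section 8.2 and name the test for the binary endpoint. Section 8.1 should state the power of that endpoint at 70 randomized.

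The cost is a few sentences, with no new samples, visits or patients. The downside is one more supportive result to report, in PTH units, which may be less sensitive than the binary test if the effect is confined to a subset.
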